Bone Marrow Aspirate Concentration in Posterior Cervical Fusion

Specific Aim:

1) Measure the rate of bony fusion in high-risk patients undergoing posterior cervical decompression and fusion.

Hypothesis: Bone marrow aspirate concentration combined with locally harvested autograft results in equivalent rates of bony fusion, as compared to current best practice in high-risk patients undergoing posterior cervical decompression and fusion.

Outcome Measures

Primary Outcome Measures: Rate of fusion – (6, 12, and 24 months) *Rate of fusion will be assessed by flexion extension X-rays at routine follow-up, translation method (<2mm) and/or by computed tomography (CT) scan at 2 year post-operatively.*

Secondary Outcome Measures: Short Form 36 (SF-36), Neck Disability Index (NDI), Myelopathy Disability Index (MDI), and modified Japanese Orthopedic Association score (mJOA) (pre-operative, 3 months, 6 months, 12 months, and 24 months), rates of intraoperative and post-operative complications, and rates of reoperation.

Significance and Biological Relevance: Spine surgery has increased substantially in the U.S. during the past decade, with an estimated 100,000 patients undergoing cervical procedures annually.¹ As the demographics of an aging population begin to increase their utilization of healthcare resources, surgeons will undoubtedly be faced with an increasing number of high-risk patients. Osteoporosis, rheumatoid arthritis, smoking, and obesity have all been shown to be significant risk factors for surgical complications following spinal arthrodesis.^{3,5,6} Nicotine has a direct inhibitory effect on autologous cancellous bone graft revascularization, significantly increasing the rate of bony non-union.^{3,18} Similarly, obesity has been demonstrated to represent a significant risk factor for subsequent pseudoarthrosis and has been linked to nearly a 100% higher in-hospital complication rate.^{10,11}

Achieving solid bony fusion following cervical arthrodesis has long been considered the most important primary outcome measure. Non-union or pseudoarthrosis following cervical instrumentation can lead to persistent neck pain and/or recurrence of myeloradiculopathy.¹⁶ The incidence of bony fusion is affected by both patient systemic factors and local biologic environment. Significant resources have been invested into studying local environment following spinal arthrodesis, with a particular focus on high-risk patients.^{7,14,15} While rhBMP has been demonstrated to improve osseous fusion in both pre-clinical and clinical studies, increasing concerns over safety and cost efficacy have resulted in a decrease in rhBMP utilization.

Autogenous iliac crest bone graft has long been considered the current “gold standard” for use in spinal fusion surgeries because its osteogenic, osteoinductive, and osteoconductive properties are ideal for promoting fusion from a biological perspective.² However, there are numerous well-acknowledged complications associated with harvesting iliac crest, such as chronic pain, nerve injury, and pelvis fracture. To circumvent these complications, allograft bone graft alone, was proposed as a viable alternative, but it has its own shortcomings due to lack of osteoinductive factors.

Bone marrow aspirate (BMA) concentration represents a potential osteoinductive alternative to rhBMP.² BMA can be easily obtained with a needle or through a minimal incision and it contains hematopoietic cells and mesenchymal stem cells (MSC).¹² BMA can be used immediately during the operation, usually in combination with a carrier such as cadaveric allograft or demineralized bone matrix, or can be subjected to further processing to concentrate MSCs, platelet-rich plasma, or CD34+ cells. MSCs exhibit potency to differentiate into mesenchymal tissues, including bone, cartilage, muscle and adipose tissue.⁴ Multiple authors have reported good clinical outcomes with difficult osseous non-unions^{8,9,17} of the extremities or jaw, yet the quality of evidence supporting the efficacy of BMA concentration during surgical management of degenerative spine disease remains limited.^{2,13} With the recent shift in medicine towards a value-based system, demonstration of cost-effectiveness in tandem with clinical efficacy is of paramount importance. The results of this study will provide not only benchmark data for further modeling an incremental cost-effectiveness ratio, but more importantly determine whether bone marrow aspirate concentration can reliably improve bony fusion in a high risk patient population undergoing posterior cervical arthrodesis.

Approach: A prospective single institution non-blinded randomized trial. Patients with symptomatic cervical myelopathy or radiculopathy amenable to management with a posterior cervical decompression and fusion will be recruited to enroll in the study in either the outpatient or inpatient setting by an orthopaedic or neurosurgery physician. As part of standard

of care pre-operative work-up patients will undergo cervical MRI and or cervical CT myelogram with plain cervical X-rays, in addition to a detailed physical examination, demographic data and outcomes questionnaires, including the Neck Disability Index (NDI), Short Form 36 (SF-36), (Myelopathy disability index (MDI), and modified Japanese Orthopedic Association (mJOA) score). These outcomes measure sensibility, motor strength, bladder function and one's ability to perform specific tasks such as rising from a chair, performing fine-motor tasks and personal hygiene practices. All pre-operative imaging again is done as part of the standard of care and often times is done prior to patient referral for surgical consultation

Inclusion criteria will include cervical alignment allowing management with a posterior approach. Post-operative X-rays scans will be obtained at the 6-week, 12 week, 6-month, 12 –month and 24 month time points as part of the standard post-operative assessment. Detailed physical exams and patient reported questionnaires (NDI, SF-36, MDI, mJOA) will be obtained at these follow-up points.

100 consecutive high-risk patients who meet the following inclusion criteria: are 18-75 years of age, require a cervical spine MRI as part of their standard of care show evidence of CSM, and have cervical alignment allowing posterior instrumented fusion. High-risk will be defined as having a diagnosis of rheumatoid arthritis, osteoporosis, current smoker, or BMI >30. Patients will be excluded if they have any MRI incompatible devices, have any prior cervical instrumentation, require an instrumented anterior cervical fusion, or have an underlying neurological condition affecting the cervical spine (MS, ALS, HIV).

Patients will be sequentially randomized to one of two treatment groups. Group I, will receive current best practice for posterior instrumented fusion (locally harvested autograft, demineralized bone matrix, and cadaveric allograft). Group II, will receive locally harvested autograft and 20 cc of bone marrow aspirate concentration. To assist with analysis, we will collect information from patients' hematology results, obtained per their standard of care pre-operative workup. All patients will be treated post-operatively at the discretion of the treating surgeon. All patients will follow-up at 6 weeks, 3 months, 6 months, 12 months, and 24 months. At the 6, 12, and 24-month follow-up all patients will undergo flexion/extension X-rays, fusion will be defined as less than 2 mm or motion. A cervical spine CT may also be obtained at 24 months on all patients to assess fusion at the discretion of the treating surgeon. All radiographic assessments of fusion will be made by a Washington University staff radiologist, blinded to patient treatment.

Cellular Analysis: Would consist of bone marrow aspirate and bone marrow aspirate concentration total cell and nucleated cell counts performed on all patients from Group II. Analysis will be performed on 1 cc of aspirate and aspirate concentration harvested at the time of surgery. Additionally, we will measure Hematopoietic stem cell and colony-forming unit fibroblast counts and BMP-2 levels. All cellular analyses will be performed by a hired third party (Immune Disease Institute, Boston, MA) blinded to the study.

Eligibility Inclusion Criteria: Age 18 and 75, able to cooperate in the completion of standardized outcome measures (SF-36 & NDI), willing and able to comply with study protocol.

Eligibility Exclusion Criteria: Pre-existent neurologic disorder or mental disorder that would preclude accurate evaluation (psychiatric disease, Parkinson's disease, Alzheimer's disease), history of previous anterior cervical fusion at the operative site, pregnancy, active malignancy, history of previous posterior cervical decompression.

Data Management and Analysis

Data will be handled in a manner that complies with federal guidelines. Data will be stored on servers maintained by Washington University School of Medicine. This data will be password protected and only approved members of the research team will be granted access. All data management will be performed by a hired third party from Washington University Center for Clinical Studies. Case report forms (CRFs) will be managed using Redcap, a commercially available, web-based data management system. CRFs are completed by the Data entry for the study is web-based. CRFs are completed by the principle investigators and saved to the Redcap server site. All data is readily available for transfer to excel format for statistical analysis and interim evaluations.

Outcome assessments for the primary outcome measure (radiographic fusion) will be provided by staff radiologists of Washington University. The radiologist will be blinded to the clinical treatment received by each patient. Patients will provide completed SF-36 and NDI data at clinical follow-up. This data will be recorded directly by the

Center for Clinical Studies, while all statistical analysis will be performed by [name] (Biostatistics). All Staff members will randomly audit and verify 10% of the data using graphical, logic and consistency checks applied at several stages of data processing. Data that are manually collected during testing will be entered using forms designed to resemble the CRFs for enhanced accuracy.

Power Analysis: Based on our secondary outcome measures (SF-36 and NDI) preliminary estimates suggest a sample size of 50, per group, will provide greater than 80% power. This estimate was generated by the Department of biostatistics, Washington University to account for variance in the outcome score of SF-36 and NDI. It is anticipated that some patients will achieve a stable asymptomatic non-union, while some patients may fail to achieve any meaningful improvement in SF-36 and NDI scores, despite achieving solid bony fusion. Power estimates were based on a repeated measures analysis of variance (ANOVA) using PowerLib 2.02.

Timeline and Expectations: The proposed study will take 3.5 years to complete (TABLE 1). Patient recruitment will occur in a consecutive randomized fashion as described in the experimental design. Enrollment will occur during the initial 12 months and patients will be followed clinically until 2 years post-operatively. We hypothesize the results from this study will provide supporting evidence that BMAC is equivalent to the current best practice for posterior instrumented fusion in a high risk patient population.

Months	1-12	12-24	24-36	36-42
Recruitment & 1 st Assessment	X			
Surgery Group I & II	X	X		
6 week postoperative assessment	X	X		
3 month postoperative assessment	X	X		
6 month postoperative assessment	X	X		
12 month postoperative assessment		X	X	
24 month postoperative assessment			X	X
Data Analysis/Reporting Results				X

Safety monitoring plan: A Data and Safety Monitoring Committee (DSMC) will be established to address issues related to personal health information and adverse events. Each patient will be reviewed by the DSMC when third of the projected number of patients have received treatment (meet when 33, 66 and 100 patients have received treatment). The DSMC will consist 3 physicians, [name] (Neurosurgery), [name] (Neurosurgery), and [name] (Neuroradiology). Reportable events will be submitted according to IRB guidelines. The same will be reported to NIH. The DSMC will meet after 33, 66 and 100 patients have received treatment to ensure ongoing safety assessments for the duration of the study. Should there be a serious adverse event that occurs that increases the risks to the participants, the study will be stopped, an investigation will be conducted, and a findings report will be generated before the study is resumed. It should be noted that the funding institute and center (IC) may wish to establish a Data and Safety Monitoring Board (DSMB). This may be done if the IC considers the project to be ‘high risk’. If such a DSMB is established, we will follow the recommendations of the NIH appointed DSMB.

References

1. Generalized intervertebral disk degeneration throughout the lumbar spine with secondary osteoarthritis. **Int Surg** **50**:222-241, 1968 PubMed PMID: 4876816.
6. Finn R, St Hill CA: New approach to organ transplantation based on the fetal allograft. **Br Med J** **1**:1671-1672, 1978 PubMed PMID: 148939; PubMed Central PMCID: PMC1605487.

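### Only Group II undergoes marrow aspiration, but no scheduled assessment names the aspiration site and complication collection is unspecified, so harm there may be recorded incompletely and unevenly

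*Combined protocol and SAP*

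**What the plan says.** **Treatment (Approach, treatment groups).** "Group II, will receive locally harvested autograft and 20 cc of bone marrow aspirate concentration". Group I receives "locally harvested autograft, demineralized bone matrix, and cadaveric allograft", with no aspiration mentioned. Cellular Analysis agrees: samples are taken at surgery, with "total cell and nucleated cell counts performed on all patients from Group II".

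**How marrow is obtained (Significance and Biological Relevance).** The only description is general: "BMA can be easily obtained with a needle or through a minimal incision". No anatomical site is named for the trial.

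**Visits (Approach).** "All patients will follow-up at 6 weeks, 3 months, 6 months, 12 months, and 24 months". Besides X-rays, the content is: "Detailed physical exams and patient reported questionnaires (NDI, SF-36, MDI, mJOA) will be obtained at these follow-up points".

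**Complications (Outcome Measures).** The secondary outcomes include "rates of intraoperative and post-operative complications, and rates of reoperation". No definition, event list, collection method or time window follows, there or elsewhere.

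**Blinding and oversight.** The trial is non-blinded. Only the radiologist and the cell laboratory are described as blinded. Under Data Management and Analysis the investigators complete the case report forms (CRFs). Under the Safety monitoring plan a DSMC reviews patients when 33, 66 and 100 have been treated.

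**The concern.** Group II has a procedure that Group I does not have, and the plan treats complications as a comparative outcome. Nothing scheduled is directed at the place where that procedure is done. Three of the four scores look at the neck or at myelopathy. The fourth, SF-36, can fall because of pain anywhere but cannot say where the pain is. According to the Approach section, the scores include tasks such as getting up from a chair, so pain at the site could lower a score without being identifiable as the cause.

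Whether a site problem reaches the complication count then depends on what each examiner looks at and what each patient mentions, and both know the allocation. At stake are the completeness of a secondary safety outcome and what the DSMC sees at its three reviews. The intended message, under Timeline and Expectations, is that the marrow concentrate is equivalent to current best practice, and a reader of that message will want to know what the additional procedure cost the patient. Symptoms not asked about at the visits cannot be reliably recovered afterwards.

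**Working it through.** **1. The plan's own figure.** The only power statement is more than 80% with 50 per group, based on SF-36 and NDI. No effect size, standard deviation, correlation, alpha or dropout is given, so it cannot be reproduced. It does not concern complications, and this point does not depend on it.

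**2. Scheduled items set against the aspiration site.**

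| Scheduled item | Could it identify a site problem? |
|---|---|
| Cervical X-rays | No, different region |
| Physical examination | Possibly; content not stated |
| NDI, MDI, mJOA | No, neck or myelopathy |
| SF-36 | Not by location |
| Complication recording | Possibly; method not stated |
| DSMC review | Only as far as events were recorded |

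No row provides uniform, prompted capture. Two rows leave it open.

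**3. What incomplete capture would do (illustration only).** The documents give neither a site-event rate nor a capture fraction; every value below is assumed. Let b be the complication rate common to both arms, s the site-event rate in Group II and c the fraction captured, with site events independent of other complications. The Group II rate is 1 − (1 − b)(1 − sc), so the observed difference is (1 − b)·s·c. Power is for 50 per arm, two-sided alpha 0.05, normal approximation.

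| b | s | c | Observed difference | Power |
|---|---|---|---|---|
| 10% | 20% | 1 | 0.90 × 0.20 × 1 = 18 points | 63% |
| 10% | 20% | 0.5 | 9 points | 25% |
| 20% | 20% | 1 | 0.80 × 0.20 × 1 = 16 points | 43% |
| 20% | 20% | 0.5 | 8 points | 15% |
| 10% | 5% | 1 | 0.90 × 0.05 × 1 = 4.5 points | 10% |
| 20% | 5% | 1 | 0.80 × 0.05 × 1 = 4 points | 7% |

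Under-capture shrinks the difference. The formula does not cover over-attribution in the arm known to have been aspirated, which would enlarge it. Even with full capture the between-arm test is weak.

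**4. What 50 Group II patients can show descriptively.** The chance of recording at least one event is 1 − (1 − sc)^50:

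| Assumed s | c = 1 | c = 0.5 |
|---|---|---|
| 1% | 39.5% | 22.2% |
| 2% | 63.6% | 39.5% |
| 5% | 92.3% | 71.8% |
| 10% | 99.5% | 92.3% |

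If all 50 are asked and none reports an event, the upper limit of the exact two-sided 95% interval is 1 − 0.025^(1/50) = 7.1%. That statement is available only if every patient was asked.

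**The case against.** The strongest reply is that silence is not exclusion. A detailed examination takes place at every visit, post-operative complications are a named outcome, adverse events go to the DSMC, and the CRFs themselves are not part of the documents. Any of these might cover the aspiration site. This stands: a reader might infer that site events are recorded only if a patient volunteers them, but the documents show only that the method is unspecified.

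Four further inferences are tempting and also fail.

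- **That this is the only harm that differs between the arms.** Group I alone receives demineralized bone matrix and cadaveric allograft, so harms linked to those materials can differ too.
- **That the plan itself attributes serious donor-site harm to aspiration.** The background speaks of "numerous well-acknowledged complications associated with harvesting iliac crest, such as chronic pain, nerve injury, and pelvis fracture", but that concerns bone graft harvest. It describes marrow aspiration separately and attributes none of these harms to it. The passage is a reason to ask, not evidence of a rate.
- **That the comparison is biased in favour of Group II.** Without blinding, unprompted recording can miss events or over-attribute symptoms, so the direction is not established.
- **That the loss can be put in percentage points.** Taking 5-20% site pain with half captured gives 50 × 5% × 0.5 = 1.25 to 50 × 20% × 0.5 = 5 missed events, or 2.5 to 10 points. Both the rate and the capture fraction are assumed, and the sum ignores patients who also have another complication.

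It can also be said that complications are secondary and the trial was not sized for them. That is true, and it limits the weight of the point.

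**Conclusion.** The concern holds in a limited form. Aspiration is confined to Group II, no scheduled assessment names the site, and the plan does not say how complications are collected. Aspiration-site harm may therefore be recorded incompletely and non-uniformly, with bias possible in either direction. No magnitude can be given, because the documents contain no event rate; the tables above show only how results would behave under assumed values. The conclusion rests on reading the graft lists and the Cellular Analysis section as meaning that Group I is not aspirated, and on the unseen CRFs not already containing site items. If they do, the remaining step is to say so in the protocol. This is an inexpensive improvement to a secondary safety outcome and does not threaten the fusion endpoint.

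**What to change.** 1. Name the aspiration site in the protocol.
2. Add to the existing CRF, pre-operatively and at 6 weeks and 3, 6, 12 and 24 months, a 0-10 pain rating for that site and yes/no items for infection, numbness or nerve symptoms, and fracture there. Use identical wording in both arms, referring to the body region rather than to the procedure, so that Group I supplies the background level.
3. Report the pain rating separately, as change from baseline by arm. The pre-operative value is needed because patients with rheumatoid arthritis, osteoporosis or a BMI above 30 may already have pain there.
4. Count only new site events (infection, nerve symptoms, fracture) as post-operative complications. The pain score does not enter the count, so it needs no cut-off.
5. Give the Group II site-event rate with an exact 95% confidence interval as a descriptive result, not as a powered between-arm test.
6. Include the items in the DSMC listings at 33, 66 and 100 patients.

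The cost is about one minute per visit at visits that already take place, with no extra imaging or patients. The downside for the sponsor is a Group II complication rate that may look slightly less favourable.

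### The only fusion criterion the plan defines is under 2 mm of motion in an instrumented spine, so stable non-unions may be counted as fused; the optional 24-month CT has no criterion and does not settle this

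*Combined protocol and SAP*

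**What the plan says.** The Specific Aim is to measure bony fusion. The hypothesis is that bone marrow aspirate concentrate with local autograft "results in equivalent rates of bony fusion, as compared to current best practice in high-risk patients". The Timeline section repeats the expectation of equivalence.

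Under Outcome Measures, fusion at 6, 12 and 24 months is assessed on flexion/extension X-rays by the "translation method (<2mm) and/or by computed tomography (CT) scan at 2 year post-operatively". The Approach section plans those films for all patients at the three visits and says that "fusion will be defined as less than 2 mm or motion" (evidently 2 mm *of* motion). On CT it says: "A cervical spine CT may also be obtained at 24 months on all patients to assess fusion at the discretion of the treating surgeon". Readings are to be "made by a Washington University staff radiologist, blinded to patient treatment".

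The control arm is described as "current best practice for posterior instrumented fusion", and eligibility requires alignment that permits posterior instrumentation. The trial is described as non-blinded.

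The Power Analysis section says: "It is anticipated that some patients will achieve a stable asymptomatic non-union". The same sentence goes on to patients who reach solid bony fusion without a meaningful gain in SF-36 or NDI.

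Nowhere does the plan give a bridging-bone or lucency criterion, a CT definition of fusion, a rule for discordant X-ray and CT, an equivalence margin, or an analysis of fusion rates.

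**The concern.** Absence of motion and presence of bone are different things, and hardware can limit motion whether or not bone has healed. The Power Analysis itself separates a stable non-union from solid bony fusion, yet the one stated criterion cannot tell them apart.

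The direction of the error matters here. In a superiority trial, counting some non-unions as fused in both arms mainly costs power. In a trial that hopes to show equivalence, the same error raises both fusion rates, narrows the gap, and makes the hoped-for conclusion easier to reach. At stake is whether a graft with a truly lower bony fusion rate could be reported as equivalent.

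**Working it through.** **The plan's own figure.** The sample size statement is that "preliminary estimates suggest a sample size of 50, per group, will provide greater than 80% power", for SF-36 and NDI. It cannot be reproduced, because alpha, effect size, SD, within-patient correlation and dropout are not given. For a simple two-group comparison at two-sided 5%, 50 per group and 80% power correspond to a standardized difference of (1.960 + 0.842) × √(2/50) = 0.56. This does not bear on fusion; only the 50 per group is used below.

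**Inputs.** From the plan: 50 per arm, the under-2-mm rule and the equivalence hypothesis. Assumed, because the plan gives none: true bony fusion of 90% v 75%; an equivalence margin of 15 or 10 points; a 90% Wald interval lying wholly within the margin; and a range for f, the share of true non-unions that move less than 2 mm.

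**Step 1: observed rates.** Observed fusion = p + f(1 − p). With the same f in both arms, observed difference = true difference × (1 − f). At f = 0.5 the rates become 0.90 + 0.5 × 0.10 = 0.95 and 0.75 + 0.5 × 0.25 = 0.875, so a true 15-point gap appears as 7.5 points.

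**Step 2: chance of declaring equivalence.** Exact binomial enumeration, 50 per arm:

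| f | Observed difference (points) | 15-point margin | 10-point margin |
|---|---|---|---|
| 0 | 15.0 | 5% | 0.1% |
| 0.1 | 13.5 | 8% | 0.4% |
| 0.3 | 10.5 | 18% | 2% |
| 0.5 | 7.5 | 40% | 9% |
| 0.7 | 4.5 | 75% | 33% |

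At a 15-point margin the arms are truly at the margin, so every entry is a false-equivalence rate against a nominal 5%. At a 10-point margin the true gap lies beyond the margin, and the rate passes 5% only between f = 0.3 and f = 0.5. Other true rates give a similar pattern: for 85% v 70% with a 15-point margin, simulation gives 3.4%, 11.5%, 32.6% and 76.9% at f = 0, 0.25, 0.5 and 0.75.

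**Step 3: unequal shares.** Let A be the better arm and B the worse. Observed difference = (pA − pB) + fA(1 − pA) − fB(1 − pB). At 90% v 75% it shrinks only if 0.10 fA < 0.25 fB, that is, if fA is less than 2.5 times fB. With fA = 0.5 and fB = 0.2 the difference stays at 15 + 5 − 5 = 15.0 points. With fA = 0.2 and fB = 0.5 it falls to 15 + 2 − 12.5 = 4.5.

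**Step 4: partial CT.** Suppose f = 0.5, and a fraction c of patients have a CT that fully corrects the X-ray reading, with CT use unrelated to arm or fusion status. Then f becomes 0.5(1 − c). The observed difference is 7.5, 9.4, 11.3 and 15.0 points at c = 0, 25%, 50% and 100%. This can apply only at 24 months, since no CT is planned at 6 or 12.

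**The case against.** Three stronger readings are tempting, and the documents support none of them.

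*That motion is the sole route to a finding of fusion.* Both Outcome Measures and the Approach section name a 24-month CT. Motion is the only criterion defined, not the only modality. CT mitigates the problem without removing it: it may not be done, the decision to order it is not blinded, and the plan does not say what counts as fused on CT or which reading prevails.

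*That the plan admits it will count stable non-unions as fused.* The sentence in the Power Analysis explains why fusion and symptom scores can diverge. It gives no motion threshold and does not say how such patients are classified. It could even imply that non-unions will be identified in stable patients by something beyond motion. Taking stable as mechanically stable is the natural reading, since asymptomatic already covers the clinical side, but it remains an inference.

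*That the result is certain to be pulled toward equivalence.* This needs a similar f in both arms, or at least one not much larger in the better arm. Blinded reading makes a reader-driven imbalance less likely. It cannot exclude a share that depends on the graft, or CT use that differs by arm.

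It is also fair to say that the error rates are built from assumptions. No value of f has any basis in the documents beyond the word some, and changing the margin from 15 to 10 points cuts the figure at f = 0.5 from 40% to 9%.

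A last objection concerns the remedy. Nothing in the plan shows that bridging bone and lucency can be read reliably on plain films of an instrumented posterior cervical spine. This is why the added readings are proposed for a sensitivity analysis and not as a new primary definition.

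**Conclusion.** The point stands in limited form. As written, the rule can score a non-union as fused, and the CT provisions are too loose to prevent it. If f is similar in both arms, a true difference is shrunk by the factor (1 − f), in the direction of the trial's hypothesis. At 90% v 75% this fails only if f in the better arm is at least 2.5 times that in the worse arm.

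The size cannot be determined from the documents. In the illustration, false equivalence ranges from little changed (8% at f = 0.1, 15-point margin) to very serious (75% at f = 0.7, same margin), and is much lower throughout at a 10-point margin. What does not depend on these assumptions is that a motion-only endpoint supports a statement about stability, while the hypothesis is about bone. The plan should be changed on this point; confidence is medium, because the reading of stable and the similarity of f across arms are both inferred.

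**What to change.** 1. On the flexion/extension films already planned at 6, 12 and 24 months, have the same blinded radiologist also record bridging bone and hardware lucency. Pre-specify a sensitivity analysis in which fusion means under 2 mm of motion with bridging bone and no lucency.
2. Reconcile Outcome Measures with the Approach section on which modality decides the primary endpoint, and use that modality in every patient for the main comparison. State the CT criterion for fusion. Report CT results and X-ray/CT agreement separately and as descriptive only, because patients with a CT are selected by their surgeons.
3. If the primary endpoint remains motion-only, name it radiographic stability (<2 mm), and do not conclude equivalence of bony fusion from it alone.

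Cost: two extra fields on the radiology case report form, with no new imaging and no new reader. The drawbacks are imperfect reading of bridging bone on plain films, some false non-unions in the sensitivity analysis, and a narrower conclusion if item 3 applies.

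### Equivalent fusion rates are hypothesised, but the only stated power is for SF-36 and NDI, and fusion has no margin, decision rule, power or deciding time point

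*Combined protocol and SAP*

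**What the plan says.** - **Hypothesis.** Under Specific Aim, the aim itself is only to measure the fusion rate in high-risk patients. The hypothesis beneath it says that the new graft "results in equivalent rates of bony fusion, as compared to current best practice in high-risk patients". Timeline and Expectations repeats this, hypothesising that the results will give "supporting evidence that BMAC is equivalent to the current best practice for posterior instrumented fusion".
- **Primary outcome.** Outcome Measures lists "Rate of fusion – (6, 12, and 24 months". A patient counts as fused on flexion/extension X-ray (less than 2 mm of translation) and/or on CT at two years. Approach says "At the 6, 12, and 24-month follow-up all patients will undergo flexion/extension X-rays", while CT at 24 months is at the treating surgeon's discretion.
- **Reading of images.** "All radiographic assessments of fusion will be made by a Washington University staff radiologist, blinded to patient treatment".
- **Power.** Power Analysis states that "secondary outcome measures (SF-36 and NDI) preliminary estimates suggest a sample size of 50, per group, will provide greater than 80% power", and that "Power estimates were based on a repeated measures analysis of variance (ANOVA) using PowerLib 2.02". It also expects that "some patients will achieve a stable asymptomatic non-union, while some patients may fail to achieve any meaningful improvement in SF-36 and NDI scores", the latter despite solid fusion.
- **Not stated anywhere.** The combined protocol and SAP gives no expected fusion rate, equivalence margin, test or interval rule for fusion, power for fusion, deciding time point or allowance for loss to follow-up.

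**The concern.** Equivalence can be concluded only against a margin fixed before the comparative data are seen. The plan hypothesises equivalence of fusion but justifies its size on other outcomes. It also says that some patients will be discordant between fusion and those outcomes, so the questionnaire power cannot stand in for fusion power.

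With no margin, rule or single time point, any of three visits and any margin could be presented as the answer after the results are known. With X-ray and/or discretionary CT, the two groups could also be assessed by different mixes of methods. What is at stake is whether the trial can validly state its own hypothesised conclusion on its primary outcome.

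**Working it through.** **1. The plan's own figure.** The figure of more than 80% at 50 per group cannot be reproduced. Power Analysis gives no alpha, sidedness, effect size, standard deviation, within-patient correlation or contrast. Solving backwards for a single time point, with an assumed two-sided alpha of 0.05, the standardised difference detectable with 80% power is (1.960 + 0.842) × √(2/50) = 2.802 × 0.2 = 0.56. The claim may well be right for SF-36 and NDI. It is power to detect a difference in a score, which is a different quantity from power to show equivalence of two proportions.

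**2. Inputs for fusion.** From the documents: 100 patients, 50 per group, binary fusion outcome. Assumed, because the documents give none: equal true fusion rates of 80, 85, 90 or 95%; margins of ±10, ±15 or ±20 points; and equivalence concluded if the two-sided 90% confidence interval for the difference lies inside the margin.

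**3. Formula.** For each group, the Wilson limits (l, u) at z = 1.645 are

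[p + z²/2n ± z√(p(1−p)/n + z²/4n²)] / (1 + z²/n).

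The Newcombe interval for p₂ − p₁ (Group II minus Group I) runs from d − √[(p₂−l₂)² + (u₁−p₁)²] to d + √[(u₂−p₂)² + (p₁−l₁)²], with d = p₂ − p₁.

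Example: 45/50 fused in both groups. The 90% Wilson limits are 80.85% and 95.05%. The half-width is √(9.15² + 5.05²) = √(83.7 + 25.5) = 10.45 points. Even identical observed rates of 90% would miss a ±10 margin and meet ±15.

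**4. Power.** Binomial probabilities were summed over all 51 × 51 = 2,601 outcomes for which the interval lies inside the margin.

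| Margin (points) | 80% fusion | 85% | 90% | 95% |
|---|---|---|---|---|
| ±10 | 0% | 1% | 6% | 32% |
| ±15 | 21% | 34% | 54% | 85% |
| ±20 | 62% | 74% | 87% | 98% |
| Smallest margin with 80% power, 50 per group | 23 | 21 | 19 | 15 |
| Same, 40 evaluable per group (assumed 20% loss) | 26 | 24 | 21 | 17 |

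The interval method matters somewhat. With Wald intervals, power at ±15 is 21/38/61/90%, and at ±10 it is 0/2/12/48%. The pattern is the same.

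**5. Precision if fusion is only estimated.** The 95% Newcombe half-width with equal observed rates is 12.7 points at 45/50 and 15.7 points at 40/50. With 40 evaluable per group it is 14.4 points at 36/40 and 17.6 points at 32/40.

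**The case against.** The best reply is that the Specific Aim is to measure the fusion rate, which is an estimation aim, and that the closing text speaks only of supporting evidence. Read this way, equivalent is loose wording. That softens the point, and it shows that the estimation option below fits the protocol's own aim. It does not remove the point, because equivalent rates remain the explicit hypothesis and the wording recurs in Timeline and Expectations.

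Three features of the plan might be thought to fill the gap:
- The 2 mm threshold classifies a patient as fused. It is not a margin between groups.
- CT at 24 months is optional, and all three visits are listed for the primary outcome, so 24 months is not established as decisive.
- Blinded reading protects how each image is scored. It does not fix the margin, rule or time point.

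Two stronger readings are tempting and are not supported:
- A reader might infer that 50 per group is too few. The documents do not show this. At 90% fusion and a ±20 margin, power would be about 87% (90% by Wald).
- A reader might infer that a non-significant difference will be reported as equivalence. The plan neither says so nor rules it out, so no weight is placed on that possibility here.

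Nor is the figure of more than 80% shown to be wrong for SF-36 and NDI.

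**Conclusion.** The point holds and should be fixed before comparative fusion data are seen. The stated power applies to secondary outcomes only. For the primary outcome, adequacy of the sample size cannot be judged, and the plan contains no prespecified rule under which equivalence could be concluded. How much this matters numerically depends on values the sponsor has not given: across the assumed rates and margins, power ranges from 0% to 98%. The absence of a margin, rule, deciding time point and single assessment method rests on the text alone and needs none of those assumptions.

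**What to change.** 1. In Power Analysis, state that the figure of more than 80% applies only to SF-36 and NDI. Add the precision or power that 100 patients, less expected loss, provide for fusion.
2. Name one primary time point and one fusion assessment method, applied the same way in both groups and using imaging already planned for all patients. Reconcile Outcome Measures with Approach on X-ray and CT.
3. Before comparative fusion data are seen, choose one:
   - (i) Reword the hypothesis and expected conclusion as estimating the Group II minus Group I difference in fusion rate with its 95% confidence interval, in line with the Specific Aim.
   - (ii) Keep equivalence, prespecify a justified margin and the interval method, conclude equivalence only if the two-sided 90% confidence interval lies inside ±margin, and state the resulting power even if it is below 80%.
4. State that a non-significant difference is not evidence of equivalence.

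**Cost.** No extra enrolment is needed. Option (i) gives up the word equivalent and accepts an interval of about ±13 to ±16 points at 90 to 80% fusion with 50 per group. Option (ii) requires the sponsor to defend a wide margin (about 15 to 23 points for 80% power at 95 to 80% fusion) or to declare lower power. Items 1 and 2 take some drafting under either option.
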